Justification: The implementation of multimodal imaging studies during the diagnosis and follow-up of patients with endophthalmitis may help to identify, characterize, and differentiate between changes associated with host immune response, drug toxicity, or ischemia, thus opening the possibility of the implementation of early treatments leading to a better final prognosis

Problem statement

Enophthalmitis is a serious condition that can result in both anatomical and functional consequences for the eye. Despite being an inflammatory condition of the eye, little is known about the vascular changes that occur secondary to endophthalmitis. For this reason, it has been decided to investigate whether angiographic changes correlate with visual prognosis in the short or medium term, as well as the comorbidities associated with each case. Do angiographic vascular changes correlate with visual prognosis?

2.1. **Objectives and hypotheses**

2.1.1.1. **General Objectives:** To describe and investigate vascular changes associated with exogenous endophthalmitis, as well as to create a photo library where they are evidenced

2.1.1.2. **Specific Objectives**

- 1. To demonstrate the presence or absence of perivasculär exudate, vessel sheathing, phlebitis/periphlebitis, diffuse or localized hemorrhages, arteriovenous shunts, vascular closure zones, and neovessels, as well as their pattern of location (in the central or peripheral region of the retina) by means of fundus photography, optical coherence tomography, and fluorescein angiography
-
- 2. To identify and correlate the presence of incipient vascular damage that could make the microcirculation more susceptible to damage during ocular infectious processes in patients with significant personal pathological history
-

Protocol ID: CVAE 01

- 3. To describe vascular changes according to their probable etiology (ischemic, drug-mediated toxicity, and host immune response) using fundus photography, optical coherence tomography, and fluorescein angiography

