2.1.3.1. Alternate hypothesis

- The incidence of vascular changes (exudates, hemorrhages, areas of capillary closure) will be less than 50% of the cases, regardless of pathogen or treatment indicated.

3. Study design

According to the moment at which the information is collected.

- Prospective - a study where the information will be collected in the future, after the beginning of the research

3.1. According to the number of times the primary variable of interest is measured or determined.

- Longitudinal.- The primary variable of interest is measured more than once over time

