3.3. According to the analysis of the study population(S)

- Descriptive.- The researcher only has a population and describes it

4. Methodology

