4.2 Description

Patients who meet the inclusion criteria will be invited to participate in the study, who will have a history of endophthalmitis and who have clear media (clear cornea, anterior chamber cellularity + or less, vitritis + or less), one week and one month after meeting the resolution criteria established by the Mexican Endophthalmitis Group.

After signing the informed consent form

A comprehensive ophthalmologic examination will be performed, including assessment of visual acuity and intraocular pressure.

A fluorescein angiography will be performed one week after meeting resolution criteria, and one month later.

Fluorescein 10% (10mg/ml) will be injected intravenously through a peripheral line.

Fundus photographs will be taken with the Clarus 700 equipment

The pictures will be analyzed in different phases and in different areas

The changes will be compared at different times, one week after meeting the resolution criteria and one month later

Consecutive recruitment will be done

Protocol ID: CVAE 01

The data will be stored in a table in Excel 2007

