5.2. Sample size. Description of the main maneuver(s)

Best-Corrected Visual Acuity (BCVA) will be assessed according to the **ETDRS guidelines**.

The test must be performed with the patient positioned **4 meters from the backlit panel**, which must be calibrated to emit **85 cd/m²**.

Testing will be conducted in **both eyes** (including both the randomized and non-randomized eye). Each eye must be tested using a chart with a different character layout to **prevent patient memorization** when such a chart variation is possible. If not, testing must begin with the **study eye**.

Protocol ID: CVAE 01

The **total number of letters correctly identified by the patient must be recorded**, along with the **Snellen equivalent** and **LogMAR score**. The test must be conducted under **best-corrected visual conditions**.

The following conversion chart will be used to record **best-corrected visual acuity**.

Valor LogMAR	Snellen (pies)	Snellen (metros)
1.6	20/800	20/240
1.5	20/640	6/190
1.4	20/500	6/150
1.3	20/400	6/120
1.2	20/320	6/96
1.1	20/250	6/75
1.0	20/200	6/60
0.9	20/160	6/48
0.8	20/125	6/38
0.7	20/100	6/30
0.6	20/80	6/24
0.5	20/63	6/19
0.4	20/50	6/15
0.3	20/40	6/12

Valor LogMAR	Snellen (pies)	Snellen (metros)
0.2	20/32	6/9.5
0.1	20/25	6/7.5
0.0	20/20	6/6
-0.1	20/15	6/4.5
-0.2	20/12	6/3.6

To measure **Best-Corrected Visual Acuity (BCVA)**, the patient will be asked to identify the letters they can distinguish until they reach the line where they are unable to locate **at least three optotypes correctly**. The number of letters correctly identified will be recorded.

Additionally, if using vision charts that **do not begin at the 20/800 line** (the point from which letter counting for ETDRS equivalence begins), the following adjustment will be made: a specific number of letters will be **added to the patient's result**. This procedure will be carried out by the **retina fellow assigned to the case**. The assessment will be performed at **each visit** (7 days and 1 month after meeting the inactivation criteria for endophthalmitis).

Indirect Ophthalmoscopy

A detailed examination of the retina will be performed. After **pupillary dilation** with **TP Ofteno® (tropicamide 5% / phenylephrine 0.8%)**, an **indirect ophthalmoscope** and a

Protocol ID: CVAE 01

20D lens will be used for a comprehensive retinal evaluation. The brand and model of the instruments used will be at the **discretion of the principal investigator**.

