The structures to be evaluated include the **optic nerve, retina, retinal vasculature**, and transparency of the **posterior segment media**, among others. This procedure will be performed **at all study visits** by the designated clinical team.

Spectral-Domain Optical Coherence Tomography (SD-OCT)

OCT imaging will be performed using the HRA Spectralis Heidelberg, Serial # Spec-CAM-15095-S3610, with a Magnification of 30° and Software version 7.0.6.0. This will aid in evaluating the retinal condition, including central macular thickness and central retinal volume (commonly referred to as macular cube volume in OCT terminology).

A technician or delegated personnel may carry out this procedure, and will be performed at all study visits.

Fundus Photography and Fluorescein Angiography

Fundus imaging will be performed using the **Clarus 700 Zeiss**, Serial #CL700-73467, Software version 1.1.2.59261, Digital Camera Magnification 133°. Images of the **posterior pole and retinal periphery** will be captured, providing a comprehensive view of retinal integrity, the optic nerve, and its vasculature.

Fluorescein angiography will be performed subsequently to evaluate **associated vascular changes**. The patient must undergo an **8-hour fast** and have **pupillary dilation with TP Ofteno® (tropicamide 5% / phenylephrine 0.8%)**. The procedure involves preparing the patient with aseptic technique for an **intravenous injection of fluorescein dye** in an upper limb, followed by imaging with a fundus camera.

It is not essential to use a device of a specific brand or model, as long as a system with **equivalent specifications** is used consistently for the **same patient throughout the study**. The procedure may be performed by a **technician or**

Protocol ID: CVAE 01

delegated personnel, and will be conducted **at all study visits** (7 days and 1 month after meeting the inactivation criteria for endophthalmitis).

Sample size

A review of hospital medical records was conducted to identify patients diagnosed with **endophthalmitis** from **February 2024 to September 2024**, resulting in a total of **57 patients**.

Considering this data was collected over 8 months, a **proportional extrapolation** was made to estimate the number of cases in a **12-month calendar year**, yielding approximately **86 patients**.

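### The protocol does not say who grades the angiograms or mask the grader to visit, acuity or history, so the week-to-month change and the associations are open to observer bias

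*Protocol*

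**What the plan says.** **Reading of the images.** Protocol 4.2 (Description) covers it in two sentences: "The pictures will be analyzed in different phases and in different areas", and "The changes will be compared at different times, one week after meeting the resolution criteria and one month later". Neither names a reader, a reading order or what the reader may know. In 5.2, the part on fundus photography and angiography says "The procedure may be performed by a technician or" other delegated staff. That concerns taking the angiogram, not grading it.

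**What is graded.** The table in section 5 (Study variables) records periphlebitis and hemorrhages as present or absent, and closure and leakage in disc areas, at one week and one month after resolution.

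**What the gradings are used for.** Section 3.1 calls the study longitudinal: "The primary variable of interest is measured more than once over time". The Problem statement asks: "Do angiographic vascular changes correlate with visual prognosis". Specific objective 2 (2.1.1.2) links vascular damage to the patient's medical history, and objective 3 sorts the changes by probable etiology.

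**Acuity.** Section 5.2 says: "This procedure will be carried out by the retina fellow assigned to the case". By grammar this could refer only to the letter adjustment described just before it. The sentence that follows, on assessment at each visit, makes the whole acuity test the natural reading. No masking to the angiogram is stated.

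**The concern.** Whether a vessel shows periphlebitis, or where an area of leakage ends, depends on the reader. A reader who knows which image is the later one may expect less disease and score it lower. A reader who knows that the eye sees poorly, or that the patient has systemic disease, may look harder for closure and leakage. The first can produce a change over time that is not there. The second can produce a correlation with acuity or comorbidity that is not there.

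These are the study's own questions: the comparison of the two visits, the link with visual prognosis, and objective 2. With no comparison group, the gradings are the result, and nothing else in the design would offset a reader's expectation.

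**Working it through.** **1. Is a grader or masking stated anywhere?** Taking the relevant places in the protocol in turn:

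- 4.2 Description: how the images are divided for analysis and which time points are compared. No reader, no masking.
- Section 5 table: scale, instrument and timing of each finding. No reader.
- 5.1.1: devices and software. No reader.
- 5.2, fundus photography and angiography: who may acquire the images. No grader.
- 5.2, Organization: retina specialists, fellows, a medical intern and nursing staff are listed. Grading is assigned to none of them.

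The protocol is therefore silent on both the grader and what the grader knows.

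**2. The protocol's own figure.** The only computed figure is the sample size in 5.2. Its inputs are 95% confidence, a 5% margin, a proportion of 50% and a population of 86 (57/8 × 12 = 85.5).

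- n0 = 1.96² × 0.25 / 0.05² ≈ 384.15
- n = n0 / (1 + n0/86) = 70.27, rounded up to 71

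This agrees with the stated 71. It sizes the estimate of one proportion and is not affected by this point.

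**3. How large could the bias be?** The documents give no reader-error rate, so the inputs below are assumptions, apart from n = 71. Let p be the true prevalence of a finding, the same at both visits. Let m be the share of present lesions missed at month 1 only, by a reader aware of the visit. Assume no false positives and no misses at week 1.

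Apparent change = p(1 − m) − p = −p × m

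| p | m | Apparent change | Patients of 71 (71 × p × m) |
|---|---|---|---|
| 50% | 5% | −2.5 points | 1.8 |
| 50% | 10% | −5 points | 3.6 |
| 50% | 15% | −7.5 points | 5.3 |
| 50% | 20% | −10 points | 7.1 |
| 30% | 5% | −1.5 points | 1.1 |
| 70% | 20% | −14 points | 9.9 |

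**4. What masking to visit changes.** If the same share m is missed at both visits, the observed prevalences are p(1 − m) and p(1 − m), and their difference is 0. Masking does not remove reading error. It makes the error the same at both visits on average, so that it no longer looks like change. Masking to acuity and history does the same for the associations.

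**The case against.** **Silence is not a statement.** A reader might infer from 4.2 that the angiograms are graded with the visit known. The text does not say so: it fixes the time points compared, not the reading conditions, and reading rules may sit in a document that is not at hand. This stands, and it limits the point to missing protection. It does not remove the point, because the protocol sets up the comparison and the correlation and describes a reading procedure without that protection.

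**The images can be read again.** One might infer that no later analysis could repair the bias. That is not supported. The images are digital, a photo library is a general objective, and nothing says they are read only once. A masked re-reading would be possible. Only acuity cannot be measured again for a past visit.

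**The ±5% margin is no yardstick.** It is tempting to call a 10-point fall twice the stated margin. That margin belongs to a single proportion with a finite-population correction, not to a paired change between visits.

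**The direction is assumed.** Both angiograms follow resolution, so an expectation of further improvement at month 1 is plausible but not documented. This stands. The table shows a scale, not a forecast.

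**The acuity part is weak.** Section 5.2 standardises the test by ETDRS rules, distance, luminance, a stopping line and a letter count. Nothing says that the assigned fellow grades the angiograms or knows their result. The week-1 angiogram does exist by month 1, so knowledge of it is possible, but that makes this a secondary matter.

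**The design is descriptive.** Section 3.3 says "The researcher only has a population and describes it", and the hypotheses concern an incidence against 50%. So no treatment comparison is at risk. The visit comparison and the correlation are nonetheless planned.

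**Conclusion.** The point holds as a gap in protection. Gradings that rest on judgement are compared between two visits and related to acuity and history, and the protocol neither names the grader nor masks the grader to any of these. The change and the associations are therefore open to observer bias. Whether bias would occur, and how much, cannot be derived from the documents. Under the stated assumptions (50% true prevalence at both visits, 5% to 20% of present lesions missed at month 1 only) the spurious fall is 2.5 to 10 points, or about 2 to 7 of 71 patients. No comparable figure can be given for the associations. The sample size of 71 is unaffected. This is a cheap improvement to make, not a defect that invalidates the study.

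**What to change.** **Change in 4.2 (Description).** State that:

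- study images are exported under a code that carries no identity, visit, history or acuity;
- the images from both visits of all patients are shuffled into one reading list;
- one of the retina specialists already listed under Organization in 5.2 grades the lesions from that list;
- acuity and history are linked only after the gradings are recorded;
- probable etiology (objective 3) is assigned after that, with the clinical history available, since judging drug toxicity or host response may need it.

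**Secondary, in 5.2.** Where another listed fellow is free, acuity may be tested by one who has not seen that patient's angiogram.

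**Cost.** Coded file names, a shuffled list and a few protocol sentences. No added staff, visits or procedures are needed, and reading of the images for clinical care is unchanged. The downside is that study grading is batched until the last month-1 image is in. Section 4.1 takes patients attended up to December 2024, while 5.4 places the database in November and December and the analysis in December. The schedule would have to be moved to allow for this.

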4.2. Inclusion criteria

- **Patients with a history of endophthalmitis**
- Diagnosis of Endophthalmitis
 - Clinical symptoms: Pain, decrease in visual acuity, anterior chamber cells and/or vitreous turbidity, corneal edema, conjunctival hyperemia
 - Laboratory studies: B-mode USG and or positive culture
- Patients who meet the endophthalmitis resolution criteria of the Mexican Endophthalmitis Study Group
- Patients with previously signed informed consent

4.3. Exclusion criteria

- Patients who have not signed the informed consent
- Patients under 18 years.
- Patients with endophthalmitis who do not meet the resolution criteria of the Mexican Endophthalmitis Study Group

Protocol ID: CVAE 01

5. Study variables

Variable name	Independent or Dependent	Nominal /ordinal/ dimensional	Unit of measurement	Measurement instrument	Time of measurement
Visual acuity	Independent	Ordinal	logMAR	Snellen Chart	At diagnosis, one week after resolution, and one month after
Vascular changes in FAG (Areas of capillary closure)	Independent	Ordinal	Disc areas	Fluorescein angiography	one week after resolution and one month after
Vascular changes in FAG (Periphlebitis)	Independent	Ordinal	Presence or absence	Fluorescein angiography with fluorescein	one week after resolution and one month after
Vascular changes in FAG (Hejorrhages on staining)	Independent	Ordinal	Presence or absence	Fluorescein angiography with fluorescein	one week after resolution and one month after
Vascular changes in FAG (Areas of leakage)	Independent	Ordinal	Disc areas	Fluorescein angiography	one week after resolution and one month after

Isolated body	Independent	Ordinal	Presence or absence of microorgan	Medium Culture	Single. When an organism grows in the culture
---------------	-------------	---------	-----------------------------------	----------------	---

Protocol ID: CVAE 01

			ism in culture		
--	--	--	----------------	--	--

Age	Independent	Dimensional	Years completed	Interrogation	Visit 1
-----	-------------	-------------	-----------------	---------------	---------

Sex	Independent	Nominal, dichotomic	Female/ Male	Tab from the collection	Unique
-----	-------------	---------------------	--------------	-------------------------	--------

5.1.1. Measuring Instrument

Retinal Imaging and Analysis: Fluorescein angiography will be performed using the **Clarus 700 Zeiss** device (Serial # CL700-73467), with Software version 1.1.2.59261 and Digital Camera Magnification of 133°.

Optical Coherence Tomography (OCT) will be performed using the **HRA Spectralis Heidelberg**, Serial # Spec-CAM-15095-S3610, with a 30° magnification and software version 7.0.6.0.

5.1.2. Time of measurement.

5.2. Sample size. Description of the main maneuver(s)

Best-Corrected Visual Acuity (BCVA) will be assessed according to the **ETDRS guidelines**.

The test must be performed with the patient positioned **4 meters from the backlit panel**, which must be calibrated to emit **85 cd/m²**.

Testing will be conducted in **both eyes** (including both the randomized and non-randomized eye). Each eye must be tested using a chart with a different character layout to **prevent patient memorization** when such a chart variation is possible. If not, testing must begin with the **study eye**.

Protocol ID: CVAE 01

The **total number of letters correctly identified by the patient must be recorded**, along with the **Snellen equivalent** and **LogMAR score**. The test must be conducted under **best-corrected visual conditions**.

The following conversion chart will be used to record **best-corrected visual acuity**.

Valor LogMAR	Snellen (pies)	Snellen (metros)
1.6	20/800	20/240
1.5	20/640	6/190
1.4	20/500	6/150
1.3	20/400	6/120
1.2	20/320	6/96
1.1	20/250	6/75
1.0	20/200	6/60
0.9	20/160	6/48
0.8	20/125	6/38
0.7	20/100	6/30
0.6	20/80	6/24
0.5	20/63	6/19
0.4	20/50	6/15
0.3	20/40	6/12

Valor LogMAR	Snellen (pies)	Snellen (metros)
0.2	20/32	6/9.5
0.1	20/25	6/7.5
0.0	20/20	6/6
-0.1	20/15	6/4.5
-0.2	20/12	6/3.6

To measure **Best-Corrected Visual Acuity (BCVA)**, the patient will be asked to identify the letters they can distinguish until they reach the line where they are unable to locate **at least three optotypes correctly**. The number of letters correctly identified will be recorded.

Additionally, if using vision charts that **do not begin at the 20/800 line** (the point from which letter counting for ETDRS equivalence begins), the following adjustment will be made: a specific number of letters will be **added to the patient's result**. This procedure will be carried out by the **retina fellow assigned to the case**. The assessment will be performed at **each visit** (7 days and 1 month after meeting the inactivation criteria for endophthalmitis).

Indirect Ophthalmoscopy

A detailed examination of the retina will be performed. After **pupillary dilation** with **TP Ofteno® (tropicamide 5% / phenylephrine 0.8%)**, an **indirect ophthalmoscope** and a

Protocol ID: CVAE 01

20D lens will be used for a comprehensive retinal evaluation. The brand and model of the instruments used will be at the **discretion of the principal investigator**.

The structures to be evaluated include the **optic nerve, retina, retinal vasculature**, and transparency of the **posterior segment media**, among others. This procedure will be performed **at all study visits** by the designated clinical team.

Spectral-Domain Optical Coherence Tomography (SD-OCT)

OCT imaging will be performed using the HRA Spectralis Heidelberg, Serial # Spec-CAM-15095-S3610, with a Magnification of 30° and Software version 7.0.6.0. This will aid in evaluating the retinal condition, including central macular thickness and central retinal volume (commonly referred to as macular cube volume in OCT terminology).

A technician or delegated personnel may carry out this procedure, and will be performed at all study visits.

Fundus Photography and Fluorescein Angiography

Fundus imaging will be performed using the **Clarus 700 Zeiss**, Serial #CL700-73467, Software version 1.1.2.59261, Digital Camera Magnification 133°. Images of the **posterior pole and retinal periphery** will be captured, providing a comprehensive view of retinal integrity, the optic nerve, and its vasculature.

Fluorescein angiography will be performed subsequently to evaluate **associated vascular changes**. The patient must undergo an **8-hour fast** and have **pupillary dilation with TP Ofteno® (tropicamide 5% / phenylephrine 0.8%)**. The procedure involves preparing the patient with aseptic technique for an **intravenous injection of fluorescein dye** in an upper limb, followed by imaging with a fundus camera.

It is not essential to use a device of a specific brand or model, as long as a system with **equivalent specifications** is used consistently for the **same patient throughout the study**. The procedure may be performed by a **technician or**

Protocol ID: CVAE 01

delegated personnel, and will be conducted **at all study visits** (7 days and 1 month after meeting the inactivation criteria for endophthalmitis).

Sample size

A review of hospital medical records was conducted to identify patients diagnosed with **endophthalmitis** from **February 2024 to September 2024**, resulting in a total of **57 patients**.

Considering this data was collected over 8 months, a **proportional extrapolation** was made to estimate the number of cases in a **12-month calendar year**, yielding approximately **86 patients**.

Based on this projection, we decided to use the **sample size formula for proportion estimation**, as our working hypothesis suggests that the **incidence of vascular changes** will be **greater than 50%**.

The sample size was calculated using an **online proportion estimation calculator**:

<https://www.calculator.net/sample-size-calculator.html?type=1&cl=95&ci=5&pp=50&ps=86&x=Calculate>:

Result

Sample size: **71**

This means 71 or more measurements/surveys are needed to have a confidence level of 95% that the real value is within $\pm 5\%$ of the measured/surveyed value.

Confidence Level:	95%	
Margin of Error:	5 %	
Population Proportion:	50 %	Use 50% if not sure
Population Size:	86	Leave blank if unlimited population size.

Calculate  **Clear**

A total of **71 patients** were included to achieve a **95% confidence interval**, with a **5% margin of error**, a **population proportion of 50%**, and a **total population size of 86 patients**.

We will calculate **measures of central tendency** (mean, median, and mode). **Chi-square tests** will be used for qualitative variables.

Data will be analyzed using the **SPSS software, version 25**.

Organization

Human Resources:

- Retina specialists affiliated with the Retina Service
- Medical intern completing social service
- Retina fellows
- Nursing staff

Protocol ID: CVAE 01

Material Resources:

- Computer
- **HRA Spectralis Heidelberg OCT**, Serial #Spec-CAM-15095-S3610, Magnification 30°, Software version 7.0.6.0
- **Clarus 700 Zeiss**, Serial #CL700-73467, Software version 1.1.2.59261, Digital Camera Magnification 133°
- Dye
- Needles
- Plastic catheters
- Vials of fluorescein

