4.1. Place and duration

The population will be patients of the retina and vitreous service of Asociación para Evitar la Ceguera en México, attended from July to December 2024, who have a complete clinical record (age, sex, pathological personal history, non-pathological personal history, heredofamilial history, ophthalmologic history, allergies, medications, ophthalmologic examination with visual acuity, intraocular pressure at each visit), signed informed consent and with a history of exogenous or endogenous endophthalmitis with clear resolution criteria and clear means one week and one month after meeting the resolution criteria to be able to perform fluorescein angiography at both visits.

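### The target of 71 patients rests on a 12-month forecast of 86 although recruitment covers six months, and its ±5% comes only from a finite population correction to that forecast

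*Protocol*

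**What the plan says.** Section 5.2 of the protocol starts from a review of hospital records "from February 2024 to September 2024, resulting in a total of 57 patients". A proportional extrapolation "was made to estimate the number of cases in a 12-month calendar year, yielding approximately 86 patients". The 86 is entered as the population size in an online calculator with 95% confidence, a 5% margin and an assumed proportion of 50%. The conclusion is: "A total of 71 patients were included to achieve a 95% confidence interval, with a 5% margin of error".

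Four other places bear on whether these inputs fit the study:

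- Section 4.1 defines the population as patients of the service "attended from July to December 2024" with a history of endophthalmitis, resolution, and media clear enough for angiography at one week and at one month.
- Section 4.2 (Description): "Consecutive recruitment will be done".
- The Justification expects the imaging to help by "opening the possibility of the implementation of early treatments leading to a better final prognosis".
- Section 3.3 calls the study descriptive: "The researcher only has a population and describes it".

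The schedule in 5.4 places data analysis in December 2024. No section gives a 12-month recruitment period.

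**The concern.** There are two separate faults.

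**Period.** The sample size takes a full year's expected cases as its base, but the study window is half a year. The target is therefore larger than the number of new cases the window should produce.

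**Precision.** A finite population correction is valid when a sample is drawn from a fixed list and the result concerns only that list. Here the 86 is a forecast and recruitment is consecutive. The Justification looks to earlier treatment, which can only concern later patients, because those enrolled have already met the resolution criteria.

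This calculation is the protocol's only basis for its number of patients and its precision, and both hypotheses (2.1.3 and 2.1.3.1) turn on whether the incidence lies above or below 50%. A margin of ±5 points suggests that an observed 55% would place the incidence above 50%. If the margin is really two to three times as wide, a result near 50% would leave the question open and readers would be misled about how firmly it had been answered.

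**Working it through.** **Inputs.** 57 diagnoses in 8 months; base of 86; 95% confidence (z = 1.96); margin d = 0.05; p = 0.50; stated n = 71 (all from 5.2). Window of six months (4.1).

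**Step 1: the protocol's own figure.**
- Monthly rate: 57/8 = 7.125. Over 12 months: 7.125 × 12 = 85.5, rounded to 86.
- Without correction: n0 = z²p(1−p)/d² = 1.96² × 0.25/0.05² = 384.1, so 385 patients.
- With correction: n = n0/(1 + (n0 − 1)/N) = 384.1/(1 + 383.1/86) = 70.4, so 71. The stated figure is reproduced.

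**Step 2: what the window supplies.**
- Six months: 7.125 × 6 = 42.75, about 43 new diagnoses before losses for resolution, clear media and consent.
- Shortfall: 71 − 42.75 = 28.25 patients, or 28.25/7.125 = 3.96 months of diagnoses.
- Time to reach 71 with no losses: 71/7.125 = 9.96 months.
- Uncertainty in the rate does not close the gap. If counts are Poisson (an assumption), the 95% interval for 57 is 43 to 74. Multiplied by 6/8, the expected six-month count is about 32 to 55.

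**Step 3: precision without the correction.** Half-width at p = 0.50 is 1.96 × √(0.25/n).

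| n | Origin | 95% half-width |
|---|---|---|
| 71 | stated target | ±11.6 points |
| 43 | six months, no losses | ±14.9 points |
| 38 | 90% of 42.75 captured | ±15.9 points |
| 30 | 70% of 42.75 captured | ±17.9 points |

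The 70% to 90% capture range is an assumption; the protocol gives no loss rate. Adding the half-width to 50%, an observed proportion of about 62% (n = 71) or 65% (n = 43) would be needed to stand clear of 50%, not 55%.

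**Step 4: how much the correction contributes.** It multiplies the half-width by √((N − n)/(N − 1)).
- n = 71, N = 86: 0.116 × √(15/85) = 0.049. The whole step from ±11.6 to ±4.9 points comes from the correction.
- The result moves with the forecast: 71 patients give ±6.3 points if N = 100, ±7.5 if N = 120 and ±9.4 if N = 200.

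**Step 5: if the result concerns only the window's patients.** With N = 43 (no net carry-over), n = 384.1/(1 + 383.1/43) = 38.8, so 39. Check: 0.157 × √(4/42) = 0.048. This needs 39/43 = 91% of all cases to be enrolled and completed.

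**The case against.** The strongest reply is that section 4.1 counts patients attended in the window with a history of the disease, not new diagnoses. Cases diagnosed before July may qualify, so 43 is not a strict ceiling. That is true, and N = 43 with n = 39 holds only if there is no net carry-over. But carry-over would have to supply about 28 patients, and the protocol gives no figure for it. The study is prospective, with angiography one week after resolution and again a month later, so a case from well before July qualifies only if it resolved late. If both visits must fall in the window, as data analysis in December 2024 (5.4) suggests, late cases that cannot finish would tend to offset early ones at a steady rate. Even counting every diagnosis from February to December, 57 + 3 × 7.125 = 78.4, reaching 71 would take 71/78.4 = 91% of them.

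The second reply is that the study is descriptive, that 3.3 speaks of describing one population, and that 5.2 names a population of 86; the Justification is motivation, not a stated target of inference. This gives the list-only reading some support. It does not rescue 71, because N must then be the window's count. For N to be 86, carry-over would have to supply 86 − 42.75 = 43.25 patients, another six months of diagnoses.

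Third, the protocol states no decision rule against 50% and does not say that a corrected interval will be reported. That is fair. The 55%, 62% and 65% figures illustrate what the margin means; they are not protocol thresholds.

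**Conclusion.** The concern holds and needs correction. The arithmetic behind 71 is right for its inputs, but those inputs match neither reading of the study.

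- **If the result is to apply beyond the listed patients**, ±5 points is not delivered. The half-width is ±11.6 points at 71 and ±14.9 at 43, two to three times the stated margin.
- **If it applies only to the patients of the window**, the population should be about 43 and the sample 39, given no net carry-over.

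On either reading, the six-month window and the target of 71 cannot both stand without a carry-over that the protocol does not quantify. The conclusion rests on the protocol's own rate of 7.125 diagnoses a month staying steady, and on half-widths taken at 50% by the normal approximation. Losses for eligibility, consent and follow-up would widen the gap.

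**What to change.** Use one period in sections 4.1 and 5.2, and choose one of these:

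1. **Keep July to December 2024.** State about 43 expected diagnoses before losses and a 95% half-width of about ±15 points at 50%, with no finite population correction.
2. **Keep 71.** Extend the window until 71 are reached (about 10 months before losses) and state ±11.6 points, again without the correction.
3. **Keep the correction.** Say expressly that the result applies solely to the listed patients of the window, and use that window's count as the population (N = 43 gives n = 39). Any expected carry-over should be stated and added to N.

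Under options 1 and 2, the reported 95% interval should be computed from the achieved number without the correction, wherever its method is laid down.

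The cost is protocol wording and a less favourable stated precision. Option 1 needs no extra patients; option 2 needs a longer recruitment window.
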